#### **Phase II. RCT phase**

This phase includes baseline assessment, intervention, and end-line assessment.

##### ***Baseline assessment***

Knowledge, attitude, and practices regarding nutrition and WASH will be assessed among school adolescents through a KAP survey along with anthropometric

measurement, physical assessment, and micronutrient assessment (CBC, Zinc, Calcium,).

The observation on the eating and WASH practices of grade 6-8 adolescents will be done by the researcher during break time (lunch time) and school off timings.

### **Research Question**

1. What is the knowledge, attitude, and practices of 6-8 grade school-going adolescents regarding the importance of consuming a diverse nutrition diet?
2. What is the knowledge, attitude, and practices of 6-8 grade school-going adolescents regarding water, sanitation, and handwashing at five critical times with soap and water?
3. What is the nutritional status of 6- 8 grade school-going adolescents'?
4. What is the level of micronutrient status in 6-8 grade school-going adolescents?

### **Participants**

The study will include both 6-8 grade school-going adolescent girls and boys. The following eligibility criteria will be followed.

### **Inclusion Criteria**

- All students studying in 6, 7, and 8 grades
- Informed consent given by adolescent's mothers/immediate caretakers
- Assent given by the adolescent at baseline

### **Exclusion Criteria**

- Students leave the school during study
- Consent not given by the mother/immediate caretaker will be excluded from the analysis

### **Sample Size & Sampling Strategy**

The sample size was calculated by using PASS software. Sample sizes were estimated to change in nutritional status of early adolescent boys and girls. A sample size of 360 adolescents

(180 in each intervention and control group) will achieve 80% power assuming 42% malnutrition among students in the control arm and at least 6% reduction in the intervention arm having 90 students from each school at a two-sided 5% level of significance.

To assess the micronutrient levels (Iron, Zinc, Calcium, CBC, and Vitamin D) through a blood sample, a subset of 108 adolescents 6-8 grade school going adolescents (54 intervention group, 54 control group) from this total sample size (360) will be selected through random selection.

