**b. Dependent variables/Outcome of study**

1. Body Mass Index: All school going 6- 8 grade adolescents will undergo anthropometric measurements such as height, and weight (BMI). The measurement will be taken at baseline and end line by using WHO standard growth chart.
2. Micronutrients: Blood sample will be collected twice (baseline and end line) from a subset of 108 adolescents (54 intervention group,54 control group). The blood samples will help to assess the impact of intervention on micronutrient deficiencies (Iron, Zinc, Calcium, CBC, Vitamin D)
3. Physical examination: Physical examination like hair, skin, nail, eye (bitot spot), mouth (dental caries), and goiter will be assessed for micronutrient deficiencies at baseline and end line.
4. Knowledge, attitude, and practices regarding nutrition and WASH: a structured questionnaire will be used to collect data on nutrition and WASH-related indicators. The survey will be administered at baseline and end line. The indicator assessed will be adolescent health status and knowledge, attitude, and practices regarding nutrition and WASH practices.

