### **Study Setting**

For this study, public schools (boys and girls) in Gojra will be selected. There are 40 public schools (20 boys and 20 girls) in Gojra. We will invite the schools for study projects that fulfill the eligibility criteria (inclusion and exclusion criteria). From these willing schools, four public schools that are at least 1-2 Km away from each other (two boys and two girls) will be randomly selected via balloting. The inclusion criterion related to distance is intended to reduce contamination between schools of different arms. These four schools (boys and girls) will then be randomly assigned to either the school (one boy and one girl) with the intervention or to the school (one boy and one girl) without the intervention (Control school).

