### Data analysis plan

Quantitative variables will be described by means and standard deviations whereas median with interquartile range will be mentioned for qualitative variables. Frequencies and percentages will be calculated for the knowledge, attitude, and practices of adolescents regarding nutrition and WASH. The comparison between intervention and control at baseline and end line will be performed by using paired t-test and Chi-square. For the variables that are not normally distributed, a nonparametric test McNamara will be used. Binary logistic regression and multiple linear regression will be used to assess the effect of intervention. All the statistical analyses will be conducted using SPSS version 23. A p-value less than 0.05 will be considered statistically significant.

Descriptive	Inferential

 
• Mean, SD Normally distributed
 
• Median, interquartile range Skewed distribution
 
• Percentages and frequencies of knowledge, attitude, and practices
 
	
 
• Chi-Square-McNamara knowledge, attitude, and practices
 
• T- test paired Continuous variables
 
• Binary logistic regression and multiple linear regression
 
• Proportion changes - chi-square Observational checklist
 

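### The 80% power claim does not follow from its own inputs: 180 pupils per arm and 42% vs 36% give about 21% for an unadjusted comparison

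*Protocol*

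**What the plan says.** The RCT-phase section Sample Size & Sampling Strategy introduces the calculation with "Sample sizes were estimated to change in nutritional status of early adolescent boys and girls" and names PASS as the software. It gives a total of 360 adolescents, 180 per arm, and states that this number "will achieve 80% power assuming 42% malnutrition among students in the control arm and at least 6% reduction in the intervention arm". The rest of that sentence fixes the number of pupils per school and the test level, which is two-sided 5% with 90 pupils in each. It gives no test, no correlation between baseline and end line, no ICC or design effect, and does not say whether the 6% is in percentage points or relative.

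Three other sections bear on how the figure might have been reached:

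- Study Setting makes the school the unit of allocation: "These four schools (boys and girls) will then be randomly assigned to either the school (one boy and one girl) with the intervention". That is two schools per arm.
- Dependent variables/Outcome of study has BMI assessed twice: "The measurement will be taken at baseline and end line by using WHO standard growth chart".
- The RCT-phase Data analysis plan lists paired t-tests, chi-square and a McNemar-type test (spelt McNamara), and adds: "Binary logistic regression and multiple linear regression will be used to assess the effect of intervention".

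**The concern.** A control proportion, a reduction, a number per arm and a two-sided level are all that a two-proportion power calculation needs. With all four stated, the 80% can be checked directly, and a 6-point difference near 40% is far too small for 180 per arm to detect with that power.

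The sentence is the only support for the size of the trial, and the Hypothesis section is about malnutrition prevalence, the quantity being powered. Readers and the ethics committee are told that the chance of detecting the stated reduction is four in five. If it is nearer one in five, a non-significant result is the likely outcome even when the intervention works as assumed, and it could be misread as evidence of no effect. The point concerns the prevalence contrast only, not BMI as a continuous measure, micronutrients, physical examination or the KAP scores.

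**Working it through.** **Inputs, all from Sample Size & Sampling Strategy:** n = 180 per arm; p1 = 0.42; p2 = 0.36 if the 6% is absolute, or 0.42 × 0.94 = 0.3948 if relative; two-sided α = 0.05 (z = 1.960); stated power 80% (z = 0.842).

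**1. Attempt to reproduce the 80%.** Two-proportion z-test, pooled variance under the null:

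power = Φ{ [ |p1 − p2| − 1.960 × √(2p̄(1 − p̄)/n) ] / √[(p1(1 − p1) + p2(1 − p2))/n] }

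- p̄ = 0.39; null SE = √(0.4758/180) = 0.0514
- alternative SE = √((0.2436 + 0.2304)/180) = 0.0513
- power = Φ[(0.06 − 0.1008)/0.0513] = Φ(−0.794) = **0.213**

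**2. Number needed for 80%.**

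n = [1.960 × √0.4758 + 0.842 × √0.4740]² / 0.06² = 1,036.2, so **1,037 per arm**.

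Conversely, 180 per arm gives 80% power for a drop of about 14.0 points (42% to about 28%).

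**3. Other unadjusted readings, independent pupils.**

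| Reading | Power |
|---|---|
| Unpooled variance | 0.215 |
| Arcsine | 0.214 |
| Exact enumeration of the chi-square test | 0.212 |
| Continuity-corrected | about 0.18 |
| One-sided 5% | 0.316 |
| 360 in each arm | 0.378 |
| 6% relative (42% vs 39.48%) | 0.070 |

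None comes near 0.80.

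**4. Baseline-adjusted comparison between arms.** The protocol gives no correlation r, so a range is assumed. Multiplying the variance by (1 − r²), with no clustering:

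| Assumed r | Power |
|---|---|
| 0.5 | 0.270 |
| 0.7 | 0.372 |
| 0.8 | 0.494 |
| 0.9 | 0.764 |

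Power reaches 80% when 1 − r² = 180/1,036.2 = 0.1737, so r ≈ 0.909. Comparing change scores instead, with variance multiplied by 2(1 − r), needs r ≈ 0.913.

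The threshold is approximate because the outcome is binary. If the intervention arm starts at 42% (an assumption) and ends at 36%, its correlation cannot exceed (0.36 − 0.42 × 0.36)/√(0.2436 × 0.2304) = 0.88. A common r of 0.909 is then unattainable in that arm, and the control arm's correlation would have to be higher still.

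**5. School randomisation.** No ICC is given, so these figures are illustrations. With 90 pupils per school the design effect is 1 + 89 × ICC. Normal reference:

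| Assumed ICC | Design effect | Unadjusted power | Detectable drop at 80% |
|---|---|---|---|
| 0 | 1.00 | 0.213 | 14.0 points |
| 0.01 | 1.89 | 0.133 | 18.9 points |
| 0.02 | 2.78 | 0.103 | 22.5 points |
| 0.05 | 5.45 | 0.072 | 30.1 points |

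For the adjusted comparison the relevant quantity is the residual ICC after baseline. At r = 0.9 and an assumed residual ICC of 0.01, power is 0.495, and 80% then needs r ≈ 0.953. With only four schools, a school-level t reference lowers power further: 0.111 on 2 degrees of freedom, unadjusted, even at ICC 0.

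**The case against.** The best defence is that the calculation was not an unadjusted end-line comparison. The section speaks of change, pupils are measured twice and regression is planned, so a baseline-adjusted contrast is a fair reading. A strong enough correlation does bring power to 80%: about 0.91 without clustering, or about 0.953 at an assumed residual ICC of 0.01. It would therefore be wrong to say that 80% is impossible, or that it requires the complete absence of clustering. Nor does a positive raw ICC necessarily lower the adjusted figures, since stable differences between schools may be largely absorbed by the baseline measurement.

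A second route is a paired test within one arm. A McNemar test on 180 pairs with a net 6-point drop has power Φ[(0.06√180 − 1.960√ψ)/√(ψ − 0.06²)], where ψ is the proportion of pupils changing status. This is about 0.82 at ψ = 0.08, 0.725 at 0.10 and 0.436 at 0.20. It may be where the figure came from, and the authors may answer with it.

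Neither route rescues the sentence. The correlation and the discordance rate are both unstated, and both would have to reflect near-perfect persistence of status. The within-arm test also does not compare intervention with control, which is how the sentence frames the effect. The PASS file is not visible, so what was actually run remains unknown, and the remedy should start there.

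**Conclusion.** The concern holds. On the stated inputs, power is about 21% rather than 80%, assuming an absolute 6-point reduction, independent pupils and an unadjusted end-line comparison. Reading the 6% as relative gives about 7%. Positive clustering within schools lowers these unadjusted figures further. Reaching 80% needs an unstated and very high baseline to end-line correlation, or a different test with an unstated and very low discordance rate.

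The core result uses only figures in the protocol. The correlations, discordance rates and ICCs above are assumptions used to test alternative readings. This is not a detail that can be left to a statistical analysis plan: the protocol asserts a number that its own inputs do not support, and it must be corrected there.

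**What to change.** Retrieve the PASS inputs. In Sample Size & Sampling Strategy, state the test, whether the 6% is in points or relative, any baseline to end-line correlation and ICC used, and the power they give when four schools are randomised.

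If no such inputs exist, delete the 80% claim and write:

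> With 180 pupils per arm (90 from each of two schools), power for a reduction from 42% to 36% at two-sided 5% is about 21% for an unadjusted end-line comparison that treats pupils as independent, and lower once randomisation of four schools is taken into account.

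Any detectable difference quoted (about 14 points, 42% to 28%) should be labelled as unadjusted with ICC 0 and shown beside values for a range of assumed ICCs.

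The cost is finding one software file and rewording one sentence. No extra pupils are needed for this correction. The drawback is a less favourable stated power, which is the accurate position on the inputs given.

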educational performance among adolescents is their nutrition status (Mwaniki, 2014 & Madjdian, 2018). Healthy Nutrition results in better growth and development during infancy and adolescents. However, nutritional requirements keep changing through the period of adolescence (Zulfiqar, 2017). Almost 80 % of adolescent's growth is completed in the early adolescence phase and is associated with emotional, cognitive, and hormonal changes (WHO, 2006). Adolescents attain 50 % of their physical growth during the early adolescent period (Hossen, 2016). Their caloric requirements also reach up to 2000-3000 Kcal per day for males, while for females the requirement is 2000-2500 Kcal along with an increase in protein intake requirement of 1.1-1.2 g/kg/day (Paracha,2019). The dietary requirements of both early as well as late adolescent groups are almost the same as well as macro and micronutrients are concerned (WHO, 2006).

The study conducted in Sialkot in 2013 on three hundred twenty-eight school going adolescences of both genders revealed that the diet and nutritional status were not up to the standards of adequacy for micro nutrients (minerals), and females are more affected than males (Rifat-uz-Zaman, 2013). An increase in physical activity along with deprived eating practices and other issues like menstruation highlight the possible risk factor for adolescent's poor nutrition. The results of the research studies conclude that malnutrition leads to deprived physical and mental development, poor resistance to diseases and poor performance at school (Bhutta, 2011 & Haddad, 2015& Bundy, 2018). In addition, adolescent girls' requirement for iron intake increases due to menstrual blood loss. On the other hand, boys have increased iron intake requirement due to muscle mass accumulation along with an increase intake of calcium as the majority of the skeletal growth taking place in this period (Bundy, 2017).

Iron deficiency and anemia lead to decrease or slow cognitive functioning, lower educational achievement, and lower physical capability. Iodine deficiency causes harmful effects

like neural impairment and culminates in poor educational achievements. For healthy immune system functioning and optimal vision, Vitamin A is important. A low level of Vitamin A can negatively affect physical growth and sexual maturation. Zinc is also vital for attaining maximum growth potential (World Bank, 2003).

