2. In the RCT phase, baseline assessment of the school-going adolescents will be conducted (knowledge, attitude, and practices (KAP) regarding healthy diet and WASH practices, along with biochemical markers (Blood complete picture, Zinc, Calcium, and Vitamin D level) in subset of 180 participants from total adolescent's target study population. Furthermore, intervention focusing multi components strategies like nutrition education, deworming, Water, Sanitation, and Hygiene will be implemented for 6, 7, and 8 grade school going early adolescents. For the Adolescents mothers/Immediate care taker cooking recipe books will be provided in the local context based on Pakistan dietary guidelines. Workshop will be arranged for school teachers to train them as master trainer. In the end line of the study, KAP evaluation and biochemical, markers will be done to assess the effectiveness of the intervention.
3. Dissemination phase or research uptake

Pakistan has significantly high incidence of malnutrition, which needs to be explored and addressed in early adolescents. Poor nutritional status in children leads to lot of physical and mental problems during this phase of life and afterword. Healthy Nutrition result in better growth and development during this period and is a second window of opportunity for catch up growth who have already experienced stunting (Bundy,2018 & WHO,2014). According to Hossen, “well-nourished adolescents at present can make optimal use of their skills, talents, and energies and be healthy, responsible citizens and parents of healthy babies” (Bhutta,2014 & Hossen,

2016). Hence, for their physical and mental development a good nutrition has a major role to play (Bundy et al., 2018).

Therefore, this study is designed to assess the effect of Nutrition education and water, sanitation, and hygiene intervention on school going early adolescent girls and boys in Gojra, Pakistan and to suggest ways how to overcome this health issue.

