### **Eligibility criteria for public schools**

#### **Inclusion criteria**

- Schools that have functional facilities of WASH will be selected.
- Single-gender schools will be selected
- Schools that will give informed consent to participate in the study

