**Post-intervention phase (Duration 2 months)**

End line Assessment	KAP survey	Early school adolescents (6,7,8 grade)	Researcher	KAP survey questionnaire
	Anthropometric measurement (BMI)	Early school adolescents (6,7,8 grade)	Researcher	
 
• Height scale
 
• Weight machine
 
• WHO growth chart
 

	Micronutrient assessment (Blood complete picture, Zinc and Calcium)	30 % of the total Adolescents sample (108 participants, 54 from each group)	LAB (Aga Khan Lab)	Blood test from Lab
	Physical assessment (skin, hair, eyes, nail, tongue, teeth, gums,)	Early school adolescents (6,7,8 grade)	Researcher	Checklist
	Observation (Eating and WASH practices) at School	Early school adolescents (6,7,8 grade)	Researcher	Observation Checklist
Dissemination Phase				
	Research uptake	Stakeholders (adolescents, mother/immediate caretakers, school teachers, school management. community stakeholder	Research team	Health mela, health screening, publication

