#### **Data collection process**

The principal investigator will collect data. Initially, a meeting with the school principal and teachers will be done to share the overall scope and objectives of the study and to seek their cooperation throughout the study. Secondly, to approach 6, 7, and 8-grade adolescents, informed consent will be first taken from their mothers/immediate caretakers and school management. Before collecting the data, a written informed assent will also be taken from the participants available in Urdu and English or the local language. Study participants will be briefed about the purpose of the study and assured about anonymity and confidentiality of the information shared. Finally, the survey questionnaire will be completed which will take around 25-30 minutes. In case, participants have any queries related to the questionnaire, an explanation will be provided

to them. Physical assessment will be done by the principal investigator which will take almost 10 minutes/ individual. For the biochemical markers assistance from the local Aga Khan Laboratory will be sought phlebotomists /lab assistants from the Aga Khan laboratory will go to the concerned educational institute and draw blood samples from the participants who have given their consent for the test.

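### The blood subset is fixed at 54 per arm with no quota per school or sex and no stated order for test consent; drawing 27 per school from consenting pupils costs nothing

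*Protocol*

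**What the plan says.** **Size and selection.** The Phase II section on sample size and sampling sets the subset as "54 intervention group, 54 control group) from this total sample size (360) will be selected through random selection". The outcome section repeats the split by arm, "subset of 108 adolescents (54 intervention group,54 control group", and the end-line table describes it as "30 % of the total Adolescents sample (108 participants, 54 from each group". None of these places gives a number per school, sex or grade. The Introduction's outline of the RCT phase has a different size: biochemical markers "in subset of 180 participants from total adolescent's target study population".

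**Structure of the arms.** The school inclusion criteria state "Single-gender schools will be selected". Under Study Setting, one boys' and one girls' school go to each arm. The sample-size paragraph has the main sample "having 90 students from each school at a two-sided 5% level of significance". So each arm holds 90 boys and 90 girls, and within an arm sex and school are the same thing.

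**Who is bled.** The Phase II data collection section says laboratory staff will "draw blood samples from the participants who have given their consent for the test". It does not say whether this consent is obtained before or after the random draw, and it has no rule for refusals.

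**Use of the subset.** The secondary objective, the effect on micronutrient levels, rests on these pupils alone.

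**The concern.** The main sample is balanced by sex within each arm by construction. The subset that carries the secondary objective is not held to that balance. The protocol gives a reason to think sex is relevant: the Introduction reports a survey of school adolescents in which mineral adequacy was poor and "females are more affected than males". A chance difference in sex mix between the two sets of 54 would then add noise to a micronutrient comparison that a school quota would avoid.

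The second gap is procedural. A fixed 54 per arm, a random draw and a consent filter fit together only if the order and the handling of refusals are stated. Without that, refusals either shrink the subset or are made good by a rule chosen in the field. The formative-phase data collection section already speaks of intervention and control schools, so allocation may be known before the Phase II consent, and no masking is described. What happens at the blood draw cannot be repaired later in an analysis plan.

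**Working it through.** **Plan's own figure.** 0.30 × 360 = 108 and 0.30 × 180 = 54 per arm, so the stated 30%, 108 and 54 agree with each other. They do not agree with the 180 in the Introduction.

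**Sex mix under the draw as written.** Inputs: 180 pupils per arm, 90 of them girls, 54 drawn without stratification, arms independent. The number of girls is hypergeometric.

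- Mean = 54 × 90/180 = 27.
- Variance = 54 × 0.25 × (180 − 54)/(180 − 1) = 13.5 × 126/179 = 9.50; SD = 3.08; 95% range 21 to 33.
- SD of the between-arm difference in share = √2 × 3.08/54 = 8.1 percentage points.
- A difference above 10 points means at least 6 girls (6/54 = 11.1 points): exact probability 0.206.
- A difference above 15 points means at least 9 girls (9/54 = 16.7 points): exact probability 0.051.

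**Effect on an arm contrast.** The shift in an unadjusted end-line contrast is the sex difference in SD units times the difference in share. The 95% edge of the share difference is 1.96 × 8.1 ≈ 15.8 points. The protocol gives no sex difference for any of its blood markers, so 0.3 to 1.0 SD is an assumption.

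| Assumed sex difference | Shift at the 95% edge |
|---|---|
| 0.3 SD | 0.3 × 0.158 = 0.05 SD |
| 0.5 SD | 0.5 × 0.158 = 0.08 SD |
| 0.8 SD | 0.8 × 0.158 = 0.13 SD |
| 1.0 SD | 1.0 × 0.158 = 0.16 SD |

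For scale, the difference detectable with 54 per arm at 80% power and two-sided 5%, ignoring clustering, is (1.960 + 0.842) × √(2/54) = 0.54 SD.

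**If the subset were 180 instead.** Assuming 90 per arm: variance = 90 × 0.25 × 90/179 = 11.3, SD 3.36, and SD of the share difference = √2 × 3.36/90 = 5.3 points. The point is the same but smaller, and the quota would be 180/4 = 45 per school.

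**With a quota.** 108/4 = 27 per school gives 27 boys and 27 girls in each arm. The sex difference at selection is then exactly zero at the same total.

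**Refusals.** The protocol gives no refusal rate; 10%, 20% and 30% are assumed. Without replacement, 54 × (1 − r) leaves about 49, 43 and 38 per arm. To end with 27 per school, 27/(1 − r) gives 30, 34 and 39 pupils to be approached. If all 90 in a school are asked first, 30% refusal still leaves 90 × 0.70 = 63 to draw from. The size of any volunteer effect cannot be computed from the document.

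**The case against.** The protocol is silent on stratification; it does not rule it out. A draw within schools would comply with its wording, and an operations manual might specify one. That stands, and it is why the point is that no stratification is stated.

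The sex imbalance is random, modest and largely recoverable. Blood is taken at baseline and end line, so a constant difference in level between the sexes drops out of a comparison of changes. The analysis section already plans multiple linear regression, where sex could be a covariate. This also stands, and it limits the first half of the point to avoidable noise.

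Three stronger readings are tempting, and the document does not support them:

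- **Pupils are drawn first and asked afterwards, with refusers replaced by volunteers.** The data collection section gives no such order. It says caretaker consent comes first and that assent precedes data collection, which is compatible with test consent before the draw. No replacement is mentioned anywhere.
- **The subset is biased between arms.** Different willingness to give blood in the two arms is possible, but nothing in the document shows it or bounds it. Bleeding only consenting minors is an ethical requirement, not a defect.
- **Iron needs are shown to differ by sex.** The Introduction says requirements rise in girls and in boys, for different reasons, and gives no difference in size. Its statement that females fare worse comes from one survey of diet and nutritional status and gives no figure for the trial's markers.

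It is also fair to say that a school quota leaves differences between individual schools mixed with the arm difference, since each arm has one school of each sex.

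**Conclusion.** The point holds as a low-cost improvement to the sampling rule and a gap in the consent procedure. It is not a demonstrated bias. As written, the draw lets the share of girls differ between arms with SD 8.1 points. The resulting shift in an unadjusted end-line contrast is about 0.05 to 0.16 SD at the 95% edge, and less with baseline comparison or adjustment for sex. This rests on 90 pupils per school, 54 drawn per arm without a quota, and an assumed sex difference of 0.3 to 1.0 SD.

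On consent, what is established is only that its timing relative to the draw and the handling of refusals are not stated. Separately, 180 and 108 for the same subset are a plain contradiction.

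**What to change.** In the Phase II sample-size section, replace the sentence on the blood subset with wording such as: *Consent and assent for the blood test are sought from all 360 pupils together with the main consent, before the subset is drawn. From the pupils who agreed in each of the four schools, 27 are drawn at random from a computer-generated list (108 in total), with ordered reserves from the same school list. Refusals, and any use of reserves, are reported by arm.* Reconcile the 180 in the Introduction with 108 throughout; if 180 is meant, the quota is 45 per school.

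The cost is a wording change, one extra item at the consent visit and a short tally of refusals. The total stays at 108. The subset will represent pupils willing to give blood, which is already the case under the present text.

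This removes sex and school imbalance at selection and leaves no room for ad hoc replacement. It does not remove a difference between arms in willingness to give blood; reporting refusals by arm only makes such a difference visible.
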